### Visit 4- Post Intervention Assessment Visit (end of the 6-week intervention):

Outcome assessments and procedure followed in Visit 1 will be repeated including questionnaires, treadmill protocol, blood sample collection and fitting of activPAL. The treadmill test will be by the investigators who are blinded to the participants group allocation. Participants will be given a prepaid envelope to return activPAL.

Post-Intervention Visit (70 mins)	Time (mins)	Responsible

a. Complete questionnaires:
 
 
1. Generic quality of life questionnaire (SF-36)
 
2. Intermittent Claudication Questionnaire (ICQ)
 
3. Visual Analogue Scale (VAS)
 
4. Geriatric Depression Scale (Short Form) (GDS-SF)
 
5. Pain Self-Efficacy Questionnaire (PSEQ)
 
6. Illness Perception Questionnaire (IPQ)
 
 
b. If participant is exiting the study at this point:
 
 
7. TENS feedback questionnaire
 
 
c. Questionnaire on adverse events of interest
	20	UA/JB
Treadmill protocol • MPQ (5 minutes post-treadmill protocol)	20	
Fitting of ActivPAL to participants and instruction for use	20	
Taking of blood sample	10	

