### 3.5 Retention Rates

The study is an intention to treat analysis and therefore if a patient does not apply the TENS or attend the education class (if randomised to this arm) they will continue to be followed up. However, all participants will have the right to withdraw from the study at any stage. If willing the reasons for withdrawal will be documented and any data already collected from that participant will be analysed.

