### Interventions:

**TENS:** Participants will be given TENS at intervention visit. They will be instructed to use the device daily at home or elsewhere. They will be specifically advised to use the device prior to, or during, a challenging walk each day. Challenging walk could be for activities of daily living (ADL) or planned exercise. For those with bilateral claudication they are advised to wear the device on the worst limb and could alternate it as symptoms fluctuates. The active group will receive High Frequency-TENS (120 Hz, 200µs and a patient-determined intensity of “strong but comfortable”).

**Placebo TENS:** Participants will receive the same model and instructions for use as those in the active group except that the stimulation dose is be safely altered to produce non-therapeutic, ineffective stimulation. For the purposes of blinding, participants will be told that different dosages of TENS are being tested some of which they might not feel anything even though the device is working. This method of effecting placebo has been successfully used in previous TENS trials.

Both the statistician conducting the randomization and the outcome assessor would be blinded to active TENS and placebo TENS. Importantly, participants will receive the same set of instructions as those in active TENS with the addition of a statement that two TENS are being tested. Blinding will be assessed at the end of the intervention period. Participants will be asked if they believed their TENS unit was functioning properly.

**Patient-Centred Education:** Intervention in these groups will be adopted from the successfully piloted SEDRIC study: A one-off three-hour workshop of structured group education (4-5 persons in each group) and three 2-weekly phone calls. Two educators will implement the session. Training for educators will involve completion of the DESMOND core training, reading and demonstrating understanding of the SEDRIC curriculum, and completion of at least two practice workshops that are

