### 8.2 Feasibility and acceptability analysis

To determine the feasibility of conducting a definitive trial, descriptive statistics will be used to report the number and proportion of participants who meet the inclusion criteria, who consented to participating, and who dropped out during the trial. Also descriptive analysis will report compliance with intervention by recording participants attendance to education session, follow up calls, attendance to TENS training session, (rate of use of TENS) rate of outcome measure completion, and total accelerometer wear time. Specifically, the TENS log (questionnaire) as well as inbuilt record of TENS device usage will both be used to analyse patients utilisation of TENS. Acceptability of TENS will be obtained by TENS feedback questionnaire

Further exploration will be carried out to determine factors that impact on propensity to participate looking at the difference in characteristics between participants and non-participants. If less than 10% of the individuals with PAD/IC in the clinic are eligible to participate, or if less than 10% of eligible patients agreed to participate, then the eligibility criteria and recruitment strategy will be adjusted prior to conducting a definitive trial. Adjustment of the recruitment strategy in a definitive trial will be made comparing the difference in the baseline characteristics between participants and non-participants. Similarly, association between participants' baseline characteristics and trial outcome will also inform decision on adjustment of recruitment strategy and stratification factors in the definitive trial. Data collection for the definitive trial will be adjusted based on the information related to type, quantity of missing data, and the mechanisms by which these data are missing.

The transcripts from the focus group discussions will be analysed using framework analysis. The data gathered from the exit interview will form part of acceptability analysis and be used to adapt the intervention to enhance its acceptability in a definitive trial.

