### **8.7 Sample size**

For the primary outcome measure, at 80% power and a two-tailed 5% significance level, 16 participants per group will allow detection of an effect size of 1.0 standard deviations of ACD in active TENS group compared to placebo control. Attrition rates in our previous pilot studies ranged from 7.1% to 10% . We will recruit 20 participants in each group, allowing for 20% attrition, and therefore aim to recruit 80 patients. If this effect size were applied to our separate pilot studies, this would provide the ability to detect a change of 169m (TENS) or 322m (SEDRIC) in our primary outcome measure of ACD. Indeed, in these studies, a sample size of 20 per group (TENS) and 14 per intervention group (SEDRIC) was sufficient to detect a significant difference in this outcome measure.

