The superiority comparison will be implemented to compare change in physical activity and PROMs between treatment groups (PE+TENS, PE+Placebo TENS, TENS) versus Placebo TENS. Also superiority comparison will be implemented for within treatment groups from baseline. A non-superiority comparison shall be made between the PE+TENS group versus each of the PE+Placebo TENS, TENS groups. The feasibility, acceptability (the recruitment, retention, outcome completion, intervention uptake and attrition rates, and patient tens feedback) and adverse events data will be summarised by randomised group and overall using descriptive statistics. No formal statistical tests comparing the randomised groups will be pre-specified. Framework analysis will be implemented for the qualitative focus group data.

Statistical analysis and stopping guidance

Interim analysis will not be conducted, and the study will stop at last patient last study visit. All outcomes will be analysed collectively at the end of the study. P-value will be set at $p < 0.05$.

Timing of outcome assessments

Physical activity and PROMs outcomes will be assessed at baseline, end of six weeks intervention (up to 2 weeks window), and 3 months post-randomisation (up to 2 weeks window). The recruitment, retention, outcome completion, intervention uptake and attrition rates will be assessed at the end of the study. Blinding and patients acceptability of TENS and

ease of use will be assessed at the point of patient exit from the study. Further assessment regarding patients' qualitative experience of intervention will be done at 3 months post-randomisation (up to 2 weeks window).

SECTION 4: STATISTICAL PRINCIPLES

Level of confidence interval and p-values

Analysis will be conducted at 95% CI, and 0.05 level of significance.

Adherence and Protocol Deviations:

Patient adherence to the intervention will be defined, as applicable, by patients attendance at the education session, and answering to at least one of the 2-weekly phone calls, and/or using TENS at least 30 mins per day 3x/wkly for at least 50% of the 6 weeks of intervention. Specifically, the TENS log (questionnaire) as well as inbuilt record of TENS device usage will both be used to analyse patients utilisation of TENS. Researcher adherence to intervention protocol will be defined as implementation of intervention and outcome assessment according to the approved study protocol.

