Measure participant's retention throughout the trial and reasons for withdrawal
Monitor, record, manage and follow-up defined adverse events in all groups
Measure uptake of intervention (log of TENS use and attendance at education) and acceptability of these interventions via a questionnaire
Measure blinding fidelity via TENS feedback questionnaire
Outcome completion rate – number of day activPAL is worn at each outcome time point.

Efficacy outcomes

Measurement will be obtained at baseline, following six weeks intervention and at 3 months follow up

Primary efficacy outcomes

Treadmill assessed Absolute Claudication Distance (ACD) (cm).

Secondary efficacy outcomes will include:

Physical activity capacity secondary outcomes

Treadmill assessed Initial Claudication Distance (ICD), assessed by a treadmill exercise using the Gardner treadmill protocol.¹⁹ Measurement will be obtained at baseline, following six weeks intervention and at 3 months follow.

Daily physical activity. We shall specify 3 days activPAL data at each measure as minimum for including patient activPAL data in the efficacy analysis. However, activPAL were time (number of day worn) will be also be reported as part of the feasibility analysis. For secondary efficacy analysis, activPAL data outcomes: total number of **i**) steps; **ii**) upright events; **iii**) walking events; **iv**) Event-based claudication index (ratio of walking events to upright events) participants undertake in a day.²⁰

PROM secondary outcomes

Disease specific quality of life will be as assessed using the Intermittent Claudication Questionnaire (ICQ).

Generic quality of life via the SF-36;

Pain quality will be recorded using the McGill Pain Questionnaire (MPQ) 5 minutes after every treadmill test.

Average Pain intensity in the past 7 days will be recorded using a Visual Analogue Scale

Illness beliefs and psychosocial determinants of health and behaviour will be recorded using the Illness Perception Questionnaire (IPQ), Geriatric Depression Scale (Short Form) (GDS-SF) and the Pain Self-Efficacy Questionnaire (PSEQ).

Qualitative Experience outcome

Analysis Methods

Feasibility and qualitative data analysis

Descriptive statistics will be used to characterize the groups at baseline and to present the feasibility outcomes.

Outcomes related to experience and perception via focus groups will be analysed by framework analysis.

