To determine the feasibility of conducting a definitive trial, descriptive statistics will be used to report the number and proportion of participants who meet the inclusion criteria, who consented to participating, and who dropped out during the trial. Also descriptive analysis will report compliance with intervention by recording participants' attendance to education session, follow up calls, attendance to TENS training session, (rate of use of TENS) rate of outcome measure completion, and total accelerometer wear time. Specifically, the TENS log (questionnaire) as well as inbuilt record of TENS device usage will both be used to analyse patients utilisation of TENS. Acceptability of TENS will be obtained by TENS feedback questionnaire

Further exploration will be carried out to determine factors that impact on propensity to participate looking at the difference in characteristics between participants and non-participants. If less than 10% of the individuals with PAD/IC in the clinic are eligible to participate, or if less than 10% of eligible patients agreed to participate, then the eligibility criteria and recruitment strategy will be adjusted prior to conducting a definitive trial. Adjustment of the recruitment strategy in a definitive trial will be made comparing the difference in the baseline characteristics between participants and non-participants. Similarly, association between participants' baseline characteristics and trial outcome will also inform decision on adjustment of recruitment strategy and stratification factors in the definitive trial. Data collection for the definitive trial will be adjusted based on the information related to type, quantity of missing data, and the mechanisms by which these data are missing.

The transcripts from the focus group discussions will be analysed using framework analysis. The data gathered from the exit interview will form part of acceptability analysis and be used to adapt the intervention to enhance its acceptability in a definitive trial.

Primary efficacy analysis

Differences in the change in ACD will be analysed and effect scores calculated using Chi-squared tests, Mann-Whitney U or Wilcoxon signed-rank tests as applicable for between and within-group comparisons and log-rank method for pooled samples or sub-strata. Baseline participants' variability will be controlled for using the analysis of co-variance.

Secondary efficacy analysis

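### The TENS feedback form is scheduled only for participants known to be exiting at Visits 4 to 6, so no scheduled form reaches those who leave earlier or who unexpectedly fail to return

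*Protocol*

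**What the plan says.** The Protocol's Study Schedule and the tables for Visits 4, 5 and 6 in section 4.1 list the TENS feedback questionnaire under one condition: "If participant is exiting the study at this point". It is listed at no other visit, and no postal or telephone version is described.

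The form carries two outcomes. Protocol section 8.2 and SAP Section 6 agree on the first: "Acceptability of TENS will be obtained by TENS feedback questionnaire". SAP Section 6 gives the second: "Measure blinding fidelity via TENS feedback questionnaire".

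The documents differ on timing. The Protocol, under Interventions, says "Blinding will be assessed at the end of the intervention period". SAP Section 3, Timing of outcome assessments, says of blinding, acceptability and ease of use together: "ease of use will be assessed at the point of patient exit from the study".

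For withdrawals, Protocol section 3.5 says: "If willing the reasons for withdrawal will be documented and any data already collected from that participant will be analysed". Section 8.2 adds: "The data gathered from the exit interview will form part of acceptability analysis", but no exit interview appears in the visit schedule. SAP Table 2 has an acceptability row and gives no rule for participants without a form.

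**The concern.** Whether TENS and education are acceptable is one of the trial's two research questions, and the answers are meant to shape the intervention for a definitive trial. For TENS, the form is the only structured measure. Holding it back until a known exit leaves two groups without one.

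- **Leaves before Visit 4.** This person attends no visit at which the form is listed. Protocol section 5 provides for withdrawal after a device-related SAR. The plan expects this to be rare, but such a person could be in this group.
- **Attends Visit 4 expecting to return, then does not.** This person has finished the six weeks and is in the clinic, but the form is deferred and never completed.

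The second group may not be small. Early recruits expect Visit 5, and every participant is invited to Visit 6, so staff at Visit 4 often cannot know who is exiting. The number of focus groups depends on data saturation, so an invited participant may never attend one.

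Those who left may hold different views from those who stayed to a planned exit. A summary of returned forms alone cannot show whether they do.

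**Working it through.** **1. The plan's own figures.** Protocol section 8.7 uses 80% power, two-sided 5% significance and an effect of 1.0 SD.

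- n per group = 2 × (1.960 + 0.842)² / 1.0² = 15.7, so 16, as stated. The t-based version gives 16.7, so 17, with power 78.1% at 16; the difference does not matter here.
- With 20% attrition: 16 / 0.80 = 20 per group, and 4 × 20 = 80. Reproduced.

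**2. How many could lack a form.** On earlier studies, section 8.7 says: "Attrition rates in our previous pilot studies ranged from 7.1"%; the upper figure is 10%, and 20% is allowed for.

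- 0.071 × 80 = 5.7, about 6
- 0.10 × 80 = 8
- 0.20 × 80 = 16, leaving 64 forms

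The documents do not split attrition into before and after Visit 4. Someone who completes every treadmill test but skips the focus group may not count as attrition at all, so deferral to Visit 6 could add to these numbers. No figure is given for that.

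**3. What the returned forms can say about all randomised.** Let d be the share without a form and p the approval among completers. Approval among all randomised lies between p(1 − d), if none of the missing approve, and p(1 − d) + d, if all do. The documents define no approval proportion and no cut-off, so p is an assumption, shown at three values.

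| d | p = 70% | p = 80% | p = 90% |
|---|---|---|---|
| 7.1% | 65.0% to 72.1% | 74.3% to 81.4% | 83.6% to 90.7% |
| 10% | 63% to 73% | 72% to 82% | 81% to 91% |
| 20% | 56% to 76% | 64% to 84% | 72% to 92% |

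The width of each range is d, whatever p is. For scale, the standard error at p = 80% with 64 forms is √(0.8 × 0.2 / 64) = 5 points, so a 95% interval is about 2 × 1.96 × 5 = 19.6 points wide. At 20% missing, the missing forms alone add about as much uncertainty as sampling does.

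**4. Direction.** Overstatement = d × (p − m), where m is approval among those without a form. At d = 20% and p = 80%:

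- m = 0%: 0.20 × 0.80 = 16 points too high
- m = 40%: 0.20 × 0.40 = 8 points too high
- m = 80%: no bias
- m = 100%: 0.20 × (−0.20) = 4 points too low

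**5. By arm.** SAP Section 3, Framework, summarises acceptability by randomised group. With 20 per arm, each missing form is 1/20 = 5 points of that arm's result.

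**6. What a form for everyone at Visit 4 recovers.** At 20% attrition and p = 80%, by how many of the 16 leave before Visit 4:

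| Leave before Visit 4 | Forms obtained | Largest possible overstatement |
|---|---|---|
| 16 | 64 | 16 points |
| 8 | 72 | 8 points |
| 0 | 80 | 0 points |

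Giving the form at Visit 4 therefore recovers nobody lost earlier. They need a separate route.

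**7. Timing.** The Protocol's end-of-intervention blinding assessment cannot be met for anyone whose form is deferred to Visit 5 or 6. Deferral also mixes answers given at six weeks with answers given about three months later on the Protocol's schedule. (The SAP counts the follow-up visit from randomisation, which would shorten that gap.)

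**The case against.** A reader might infer that drop-outs supply no acceptability data at all, and that the result is therefore biased towards approval. The documents support neither statement.

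- **Other data exist.** The SAP's exit wording is not tied to a numbered visit and can be read to cover early withdrawal, although it gives no procedure. Withdrawal reasons (if the participant is willing), the TENS log, the device's own usage record, the telephone calls in the education arms and the focus groups all bear on acceptability. None replaces the form, and withdrawn participants may not come to a focus group.
- **Stopping TENS is not leaving the trial.** Protocol section 3.5 keeps non-users in follow-up, so they can still reach the form. Only those who leave the study, or fail to return, are lost.
- **Direction is not shown.** No document gives drop-outs' views. An overstatement is plausible, but equal approval gives no bias and full approval gives a small understatement. Any fixed gap between drop-outs and completers is the reader's assumption.
- **No decision rule uses the result.** The only numerical triggers are the two 10% rules on eligibility and agreement to participate. Acceptability is descriptive, and the plan already intends to report outcome completion and to examine missing data. This limits the consequence but does not close the gap.

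A further objection is that a form for everyone at Visit 4 puts the blinding question to early recruits before their Visit 5 treadmill test. But the Protocol itself places that question at the end of the intervention period.

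**Conclusion.** The point stands as a gap in the schedule. It is a stated administration rule that, followed as written, loses forms the trial could have obtained. Up to about 6 to 8 of 80 participants at the pilots' attrition, and 16 of 80 at the planned allowance, could lack one. At 20% missing, the approval figure for all randomised is left undetermined over a 20-point range, for example 64% to 84% if 80% of completers approve.

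This rests on three assumptions: that the plan's attrition figures describe loss of forms, that staff follow the visit tables, and that some item on the form is summarised as a proportion. The completers' approval rate is illustrative. Upward bias is likely only if drop-outs approve less. Separately, the Protocol and SAP disagree on when blinding is assessed, and that holds whatever the attrition. The change is worth making, because acceptability is one of the things this trial exists to measure.

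**What to change.** - Give the TENS feedback form to every participant at Visit 4, whatever the later plan. The adverse-event questionnaire is already unconditional at that visit.
- Post the form, or complete it by telephone, for anyone who withdraws or misses Visit 4. Both steps are needed.
- Reconcile the Protocol's Interventions text with the SAP's Timing of outcome assessments on when blinding and acceptability are measured. Either place the exit interview of section 8.2 in the schedule or remove the reference.
- In the SAP Table 2 acceptability row, use all randomised participants as the denominator, count non-returned forms by arm, and give best- and worst-case bounds for any item summarised as a proportion.

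The cost is a short schedule amendment and a little postage or telephone time; pre-paid envelopes are already used for activPAL return. The reported figure may be less favourable, and some drop-outs will still not reply, so the bounds will narrow but not vanish.

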**Visit 5- Follow-up Assessment Visit (3-months post-intervention):**

All participants recruited within first eight months of recruitment will be invited to return for a 3-month follow-up visit. Outcome assessments and procedure followed in Visits 1 and 4 will be repeated including questionnaires, treadmill protocol, blood sample collection and fitting of activPAL. The treadmill test will be by the investigators who are blinded to the participants group allocation. Participants will be given a prepaid envelope to return activPAL. We shall allow assessment visit window of  $\pm$  2 weeks.

Follow-up Assessment Visit (70 mins)	Time (mins)	Responsible

Complete questionnaires:
 
 
1. Generic quality of life questionnaire (SF-36)
 
2. Intermittent Claudication Questionnaire (ICQ)
 
3. Visual Analogue Scale (VAS)
 
4. Geriatric Depression Scale (Short Form) (GDS-SF)
 
5. Pain Self-Efficacy Questionnaire (PSEQ)
 
6. Illness Perception Questionnaire (IPQ)
 
 
If participant is exiting the study at this point:
 
 
7. TENS feedback questionnaire
 
	20	UA/JB
Treadmill protocol • MPQ (5 minutes post-treadmill protocol)	20	
Fitting of ActivPAL to participants and instruction for use	20	
Taking of blood sample	10	

